3.4 Assessment of Objectives

3.4.1 Immunogenicity

The *primary objective* is to investigate the immunogenicity of Human-cl rhFVIII.

The *primary endpoint* is the incidence of inhibitors within the observation period. For one patient an inhibitor is assessed to be positive if the modified Bethesda assay (Nijmegen modification) results in a titer ≥ 0.6 BU at any time point during the observation period.

Inhibitor activity will be determined centrally at the following time points: At baseline (Screening Visit), every 3-4 EDs until ED 20, every 10-12 EDs or every 3 months \pm 2 weeks after ED 20 (whichever comes first), at study completion; at any time in the case of a suspicion of inhibitor development.

In case of a positive inhibitor result, an inhibitor re-testing using a second separately drawn sample should be performed centrally; the result of the second sample will be taken as the final result for the time point. Low titre inhibitors will be defined as ≥ 0.6 to < 5 BU, high-titre inhibitors will be defined as ≥ 5 BU.

Patients who develop a non-transient inhibitor will have an option to start ITI treatment. Patients developing inhibitors and not starting ITI within one year after inhibitor detection will be

withdrawn from the study. Inhibitors that 'disappear' without any clinical signs or symptoms, where no FVIII dosing increase was required, and that turn back to <0.6 BU within a period of 6 months after first detection are regarded as "transient". Patients who develop such a transient inhibitor will continue regular treatment within the study until they have reached ED 100 or a maximum period of 5 years.

Definition of inhibitor confirmation and time to inhibitor occurrence:

Occurrence of inhibitors:

For these definitions inhibitor titres determined in the central laboratory are considered.

(I1) FVIII:C high titre inhibitor occurrence is confirmed, if

inhibitor level ≥ 5 BU at one time point $t_{1,H}$ and

- inhibitor level confirmed to be ≥ 5 BU at a subsequent* time

point $t_{2,H}$ or

- retest of sample from *any* time point $t_{3,H}$ ($=t_{1,H}, t_{2,H}$ or later) confirmed to be ≥ 5 BU.

* 'Subsequent' in the context of this document always means 'at a later time point' or 'in a later sample', but not necessarily the immediate consecutive visit or sample.

(I2) FVIII:C Inhibitor occurrence in a patient is confirmed, if

- a high titre inhibitor is confirmed according to (I1)

or if

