- inhibitor level ≥ 0.6 BU at one time point $t_{1,I}$

and retest of sample from same time point $t_{1,I} \geq 0.6$ BU

and inhibitor level ≥ 0.6 BU at a subsequent time point

or

- inhibitor level ≥ 0.6 BU at one time point $t_{1,I}$

and inhibitor level ≥ 0.6 BU at a subsequent time point

and retest of sample from same time point $t_{2,I} \geq 0.6$ BU

or

- inhibitor level ≥ 0.6 BU at three subsequent time points $t_{1,I}, t_{2,I}$ and $t_{3,I}$
(e.g. if retests are not available).

(I3) An inhibitor is confirmed to be a low titre inhibitor, if

- occurrence of inhibitor of < 5 BU is confirmed (according to I2) but

- occurrence of high titre inhibitor (according to I1) is *never* confirmed during the observation period*

(Note: a low titre inhibitor which turns to a confirmed high titre inhibitor according to definition I1 is solely counted as a high titre inhibitor. Inhibitors initially measured as low titre of < 5 BU and remain low titre (< 5 BU) are defined as low titre inhibitors)

*This condition means that a patient only can be defined as having either a low titre inhibitor or a high titre inhibitor. The patient cannot be counted twice.

These definitions for confirmation of positive inhibitors and for high and low titre inhibitors are considered to be relevant for the overwhelming number of inhibitor occurrences. However, there might be cases where additional information (e.g. when taking the whole sequence of inhibitor testing or additional local lab data into account) may suggest that an inhibitor may be assessed rather high titre than low titre. All inhibitor data will be reviewed during the Data Review Meetings before interim analysis/ final analysis to identify such cases.

Time and number of EDs until inhibitor occurrence:

(I4) The time / number of EDs to inhibitor occurrence is defined

- by the time between ED1 and the date of the first positive inhibitor titre detected in a confirmed

inhibitor patient (I2)

- more exactly : as

minimum {date of $t_{1,H}$, date of $t_{1,I}$ } – date of Day 1 (ED1) (days) ,

or the number of EDs (with injections for any indication) during this time frame (ED1 until day before minimum {date of $t_{1,H}$, date of $t_{1,I}$ })

(Note: If different dates for $t_{1,H}$ and $t_{1,I}$ are available, the earlier date will be taken into account)

Censoring: Time / number of EDs until any inhibitor will be censored for patients without inhibitor at date of last available inhibitor testing

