For an analysis “time / number of EDs to inhibitor occurrence” for high titre inhibitors the time defined under (I4) will be applied even if the inhibitor had started as minimum {date of $t_{1,H}$, date of $t_{1,I}$ }. For this analysis patients with confirmed low titre inhibitor will be censored at date $t_{1,I}$, where the low titre inhibitor is first detected.

For an analysis “time / number of EDs to inhibitor occurrence” for low titre inhibitors the time defined under (I4) is $t_{1,I}$. For this analysis patients with confirmed high titre inhibitor will be censored at minimum {date of $t_{1,H}$, date of $t_{1,I}$ } where the high titre inhibitor is first detected.

Peak inhibitor titre:

The peak inhibitor titre for each individual patient is defined as the maximum inhibitor titre measured by central lab at any timepoint during the study. This includes also the results of re-tests.

Inhibitor-free period:

An inhibitor is regarded as confirmed between start date as defined above (Definition “I4”) and the time when the inhibitor titre decreases back to <0.6 BU for the first time, which is to be confirmed by a subsequent measurement of <0.6 BU. If the inhibitor titre does not decrease to <0.6 BU during the study, the period with confirmed inhibitor will be counted until study end. Periods of time without confirmed inhibitor are regarded as “inhibitor-free”.

Prophylactic Treatment

Secondary objective: To assess the efficacy of Human-cl rhFVIII during prophylactic treatment.

Secondary endpoint: Monthly rate of spontaneous break-through bleeds during time of prophylactic treatment assessed as excellent, good, moderate or poor by the following scale:

Excellent: Less than 0.75 spontaneous BE per month.

Good: Between 0.75 and 1 spontaneous BE per month.

Moderate: Between more than 1 and 1.5 spontaneous BEs per month.

Poor: More than 1.5 spontaneous BEs per month.

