The time period for prophylactic treatment will comprise the time periods between first prophylactic treatment with *Human-cl rhFVIII* until the administration of the last prophylactic treatment + 14 days or completion visit (whichever comes first) minus time periods from start of a surgery until final assessment of the surgery, and minus time period of on-demand treatment, if any. All spontaneous BEs starting during the time periods for prophylactic treatment defined above will be included. BEs categorized as traumatic or as post-operative will not be included in the primary prophylactic treatment assessment.

Regarding BEs during or after surgery this is a general rule.

However, BEs emerging shortly after surgeries could be independent from the surgery, whereas a surgery-related BE could still emerge after the final assessment of the surgery. Therefore the final assessment of whether or not the BE is related to surgery (i.e. to be categorized as post-operative), and hence will be excluded from the BE incidence calculation for prophylactic treatment, will be made in the data review meeting before final database close.

In addition to the analyses described above, the analyses of bleeding rates will be performed in all patients during inhibitor-free periods.

Study drug consumption data (FVIII IU/kg BW, extrapolated to monthly and yearly usage) per subject will be evaluated.

3.4.2 **Bleeding Episodes (BEs)**

Secondary objective: To assess the efficacy of *Human-cl rhFVIII* during treatment of bleeds

Secondary endpoint: Efficacy assessment of bleeding episodes at end of a BE on a four point scale by the patient's parent(s)/legal guardian(s) (together with the Investigator in case of on-site treatment):

- Excellent:* Abrupt pain relief and/or unequivocal improvement in objective signs of bleeding within approximately 8 hours after a single infusion
- Good:* Definite pain relief and/or improvement in signs of bleeding within approximately 8 – 12 hours after an infusion requiring up to 2 infusions for complete resolution
- Moderate:* Probable or slight beneficial effect within approximately 12 hours after the first infusion requiring more than two infusions for complete resolution
- None:* No improvement within 12 hours, or worsening of symptoms, requiring more than 2 infusions for complete resolution

For all breakthrough BEs occurring during the study period, the following data will be documented or derived:

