- Number of subjects treated prophylactically
- Characteristics and number of prophylactic treatments: Treatment intervals, dosage, changes or interruptions in prophylactic treatments
- Number of injections and exposure days. Injections administered over midnight will only count as exposure day on the day on which the injection had started.
- Amount of *Human-cl rhFVIII* used (per month, per year*, exposure day and injection, and in total)

*projected estimate

- Overall efficacy assessment at the end of the study: Number and rate (per month and per year) of spontaneous BEs in subjects on prophylactic treatment*; in total, as well as broken down to intensity of prophylaxis, timely distance from last study drug administration, dose(s) and characteristics of BE (type, site and severity of BE).

*The rate of BEs will exclude BEs and the time period between start of surgery-related prophylactic treatment and re-start of prophylactic treatment after surgery.

It will also exclude BEs and time periods of “on-demand” treatment, if any.

- In two additional secondary analyses, overall efficacy analysis for prophylactic treatment will be analysed
 - for traumatic BEs
 - for all BEs (spontaneous, traumatic, others (if any)).
- Further analysis on bleeding rates will be performed in patients who developed an inhibitor, but only during their inhibitor-free periods. An inhibitor is regarded as confirmed between its start date, as defined in Chapter 3.4.1, Definition “I4”, and the time when the inhibitor titre decreases again to <0.6 BU for the first time, which has to be confirmed by a subsequent measurement of < 0.6 BU; should the inhibitor titre however not have decreased to < 0.6 BU during the study the period with confirmed inhibitor lasts until the end of the study. Periods of prophylaxis without confirmed inhibitor are regarded as “inhibitor-free”.
- Study drug consumption data for prophylactic treatment (IU FVIII /kg BW per month, per year, exposure days) per subject and in total (for subjects on prophylactic treatment) will be presented descriptively.

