10.1 Complete success of ITI therapy

Complete success of a patient’s ITI will be defined as:

- FVIII:C inhibitor negative (<0.6 BU) (at two sequential measurements)
- Recovery ≥ 0.99 %/(IU/kg BW) (= 66% of 1.5 % (IU/kg BW))
- terminal half-life ≥ 6 hours

Complete success is

- 1) documented in the “ITI Study Completion” by the investigator and
- 2) derived from the documented data on the objective criteria
 - in the inhibitor data
 - as derived from the recovery/half-life data
(central and/or local lab determinations with one-stage assay and/or chromogenic assay)

If more than one lab determination is available (e.g. local and central lab; several assays), worst available values are taken into account for the inhibitor criterion (highest titre) and the recovery criterion (lowest IVR); this also applies for the half-life criterion (lowest half-life). However, there may be exceptions when there is a difference in available data for PK analysis and one of the series of measurements is expected to provide more reliable estimations of the terminal half-life data than the other(s); if necessary, reliability of series of measurements in terms of available data for PK analysis will be assessed in data review meetings before interim and final analysis.

11 **EVALUATION OF SAFETY PARAMETERS**

11.1 **Adverse Events**

All adverse events occurring or worsening after initiation of study treatments until the completion visit (treatment emergent AEs) will be displayed in summary tables and listings.

Incidences of adverse events will be given as numbers and percentages of subjects; for AEs judged to be related to study drug or occurring during or within 24 hours of the end of an infusion also the numbers and percentages of infusions associated with such AEs will be presented:

- Any AE (by MedDRA (version 15.0 or later) preferred term (descending frequency) and by MedDRA System Organ Class (SOC))
- Any serious AE (by MedDRA System Organ Class (SOC)/ preferred term)
- Any AE probably or possibly related to the trial drug (by MedDRA System Organ Class (SOC)/ preferred term)
- Any AE temporally related (within 24 hours after end of infusion*) to the trial drug (by MedDRA preferred term (descending frequency) and by MedDRA System Organ Class (SOC))
- Any severe AE (by MedDRA System Organ Class (SOC)/ preferred term)
- Any withdrawal due to AE (Adverse drop-out)

* In case another infusion starts within the 24 hours the AE will be related to the last infusion.

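### As written, the SAP closes an inhibitor at its first titre below 0.6 BU on the strength of any later negative and never reopens it, so in patients who turn positive again, time with a measurable inhibitor is counted as inhibitor-free

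*SAP*

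**What the plan says.** SAP 3.4.1 (Inhibitor-free period) runs the confirmed-inhibitor period from the start date in definition I4 to "the time when the inhibitor titre decreases back to <0.6 BU for the first time, which is to be confirmed by a subsequent measurement" below 0.6 BU. If the titre never falls below 0.6 BU, the period runs to study end. SAP 9.2 repeats the rule for the prophylaxis analysis.

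Three other statements fix its meaning:

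- SAP 3.4.1 says that the word *subsequent* "always means 'at a later time point' or 'in a later sample', but not necessarily the immediate consecutive visit or sample", and applies this to the whole document.
- I4 measures onset "by the time between ED1 and the date of the first positive inhibitor titre detected in a confirmed" inhibitor patient, which gives one start date per patient.
- The remainder is assigned by default: "Periods of time without confirmed inhibitor are regarded as" inhibitor-free.

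For ITI success, SAP 10.1 uses different wording: "FVIII:C inhibitor negative (<0.6 BU) (at two sequential measurements".

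The scope is worded in two ways. In SAP 3.4.1 (Prophylactic Treatment), "the analyses of bleeding rates will be performed in all patients during inhibitor-free periods". In SAP 9.2, "Further analysis on bleeding rates will be performed in patients who developed an inhibitor, but only during their inhibitor-free periods".

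**The concern.** The inhibitor-free split is there to describe the product when no measurable antibody neutralises it. The definition can fail to deliver that in two ways.

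- **Dip.** One low result, followed by months of positive titres and finally a negative, is confirmed by that last negative. The inhibitor closes at the dip, and the positive months become inhibitor-free.
- **Relapse.** After a genuine clearance, a new run of positive titres has no start date to attach to, so it also stays inhibitor-free.

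Bleeds and surgeries in such time enter the inhibitor-free tables. The prophylaxis tables for time with confirmed inhibitor (14.2.19.6.8.1, 14.2.19.6.8.2 and 14.2.19.8.3) lose the same time and bleeds. Both sides of the comparison are then contaminated.

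**Working it through.** The documents give no figure on this point, so there is none to reproduce. The check applies the rule literally to assumed titre sequences and then traces where the result is used.

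**Step 1: the two rules.**

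- *SAP rule:* start at the first titre of 0.6 BU or more; end at the first later titre below 0.6 BU if any sample after that is also below 0.6 BU; no second start.
- *Comparison rule:* end at the first of two consecutive results below 0.6 BU; reopen at a later positive.

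**Step 2: assumed sequences over 15 months** (titre in BU, month in brackets).

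- A, dip: 0 (0), 2 (1), 3 (2), 0.5 (3), 4 (6), 8 (9), 0.4 (12), 0.3 (15)
- B, relapse: 0 (0), 2 (1), 1.5 (2), 0.5 (3), 0.4 (6), 3 (9), 4 (12), 3 (15)
- C, clean clearance: 0 (0), 2 (1), 1.5 (2), 0.5 (3), 0.4 (6), 0.3 (9), 0.2 (12), 0.2 (15)
- D, last sample only: 0 (0), 2 (1), 1.5 (2), 1.1 (6), 1 (12), 0.4 (15)

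Inhibitor-free months = 15 − total length of the inhibitor periods.

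| Case | SAP rule | Comparison rule | Positive samples inside SAP inhibitor-free time |
|---|---|---|---|
| A | 15 − (3 − 1) = 13 | 15 − (12 − 1) = 4 | 2 (4 and 8 BU) |
| B | 15 − (3 − 1) = 13 | 15 − (3 − 1) − (15 − 9) = 7 | 3 (3, 4 and 3 BU) |
| C | 15 − (3 − 1) = 13 | 15 − (3 − 1) = 13 | 0 |
| D | not defined | 15 − (15 − 1) = 1 | – |

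In A, the negative at month 12 confirms the dip at month 3. In B, the clearance at month 3 is properly confirmed at month 6, and the relapse from month 9 has no start date. C shows that the rules agree when no later positive occurs. D exposes a further gap: a single last negative is not confirmed, but the titre has fallen below 0.6 BU, so neither clause of the rule applies.

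**Step 3: pooled effect, on assumptions only.** Let 100 patients contribute 20 months each, k of them with m misfiled months, and let the bleeding rate be r times higher with an inhibitor. The pooled inhibitor-free rate is inflated by k × m × (r − 1) / (100 × 20).

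- k = 2, m = 3, r = 2: 2 × 3 × 1 / 2000 = 0.3%
- k = 5, m = 3, r = 5: 5 × 3 × 4 / 2000 = 3%
- k = 10, m = 9, r = 5: 10 × 9 × 4 / 2000 = 18%

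No value of k, m or r comes from the documents.

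**Step 4: where the split is used.**

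- *Bleeds.* SAP 9.3 repeats all bleed analyses for inhibitor-free periods. In the SAP section 13 table list, thirteen bleed tables appear only in that form: 14.2.27, 28.1, 28.2, 29, 31, 33, 34, 35, 36, 37, 38.1, 38.2 and 39. They cover severity, treatment duration, dose and bleed frequency. The BLEED population (SAP 5.1) includes bleeds treated under ITI, which may last 36 months.
- *Continuous prophylaxis.* The Poisson annualised rates for PROPHcont (14.2.19.7.3 and 14.2.19.7.4) are listed only for inhibitor-free periods.
- *Surgery.* SAP 9.4 repeats all analyses for inhibitor-free periods.

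**Step 5: is there a safeguard?** The data review clause in SAP 3.4.1 concerns cases where an inhibitor may be high rather than low titre. It does not mention the end or reopening of an inhibitor period.

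**The case against.** **Another reading of the rule.** The clause could mean the first *confirmed* decrease. This does not remove the problem, because under the SAP's definition any later sample still confirms. No reading supplies a reopening rule.

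**Limited consequence.** This largely stands. The primary endpoint and time to inhibitor do not use the end date. The all-period PROPH, BLEED and SURG analyses, which SAP 5.1 names as most relevant, do not use the split. Overall versions exist for the main prophylaxis tables (14.2.19.1 to 14.2.19.3) and the bleed-efficacy tables (14.2.30.1 and 14.2.30.2). The study is descriptive, and all inhibitor results are listed, so relapses stay visible.

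**Little such time on prophylaxis.** This stands in part. PROPH uses only data under prophylaxis, and ITI is a separate treatment type. Patients who do not start ITI within one year of inhibitor detection are withdrawn, and those with complete ITI success leave the study. What remains is positive time on prophylaxis before ITI, or a relapse after a transient inhibitor. Long dips during ITI bear mainly on the bleed and surgery tables.

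**Stronger readings that the documents do not support:**

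- A reader might infer from SAP 9.2 that the inhibitor-free bleeding rates cover only inhibitor patients, about 30 of 100 at the protocol's upper figure of about 30%. The table list sets those tables on PROPH, PROPH-PP and PROPHcont, none of which is restricted to inhibitor patients. The conflict with 3.4.1 is one of wording.
- A reader might infer that misclassification is certain or large. It needs a titre of 0.6 BU or more after a first negative, and the documents give no count of such patients.
- A reader might infer that the rule flatters the product. If an inhibitor raises bleeding or weakens the response, the inhibitor-free results look worse.

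**Conclusion.** Wrong as written. This is a stated rule that, followed literally, labels samples of 4 or 8 BU inhibitor-free; it is more than a missing detail.

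The fault is conditional and confined to the inhibitor-free and confirmed-inhibitor splits. For an affected patient it can be large: 13 months against 4 or 7 in the assumed sequences. Across the trial its size is unknown. The range of 0.3% to 18% is arithmetic on assumed inputs, not an estimate, and the effect is zero if no patient turns positive again after a first negative. It deserves correction because several bleed and bleeding-rate tables have no all-period counterpart in the table list.

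**What to change.** In SAP 3.4.1 and 9.2, replace the end rule with:

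> The inhibitor period ends on the date of the first of two consecutive central-laboratory results <0.6 BU with no result ≥0.6 BU between them. It reopens on the date of the next result ≥0.6 BU that is confirmed by a retest or by the immediately following sample ≥0.6 BU, and ends again by the same rule. A single last result <0.6 BU with no later sample does not end the period.

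Reopening should not refer back to definitions I1 and I2. They rely on the same any-later-sample meaning, so an isolated positive could be confirmed by a much later one.

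Report the number of patients, months and bleeds reclassified against the present rule. SAP 6.4.3 records that the interim analysis has been done, so the change should be open to inspection. As a wording clean-up, align 9.2 with the all-patients scope of 3.4.1, which matches the populations in the table list.

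The cost is SAP text and one changed derivation, with no new data. The drawbacks are a derivation changed after the interim analysis of an open-label study, and slightly less time and fewer bleeds in the inhibitor-free set.

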**Prophylactic Treatment** 

Frequency of spontaneous breakthrough bleeds under three times weekly or every other day prophylactic treatment, and in case of surgical prophylaxis

Efficacy

Efficacy assessment at the end of each BE (based on the efficacy scale described in Section 7.2.2.2)

Recovery Investigation

*In vivo* recovery (calculated from the FVIII plasma levels before infusion and the peak level obtained from the 15 minutes and 1 hour post-infusion samples)

Safety

Vital signs (blood pressure, heart rate, respiratory rate and body temperature)

Safety laboratory parameters (red blood cell [RBC] count, white blood cell [WBC] count, haemoglobin, haematocrit, platelet count, alanine amino transferase [ALT], aspartate transaminase [AST], serum creatinine)

Tolerability (occurrence of any AE will be monitored throughout the study)

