## Prophylactic Treatment

1 IU factor VIII per kg body weight raises the plasma factor VIII activity by 1.5 % to 2 %.

In case prophylactic treatment is chosen, the patients will be treated with a recommended dose of 20-50 IU FVIII/kg body weight (BW).

Starting the prophylaxis with the first BE is highly recommended.

The frequency of treatment will mainly depend on the patient's clinical situation. For example, prophylaxis may be initiated with every-other-day injections (in order to keep the FVIII trough level >1%) or with once weekly injections, followed by twice and three times weekly, and every other day treatment. In cases of inadequate response, *Human-cl rhFVIII* administration frequency or dose adjustments can be considered at Investigator's discretion.

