## 7.2.2 Assessments for Secondary Endpoints

## 7.2.2.1 Prophylactic treatment

The following parameters will be documented:

- Dates and times of study product injections
- Details of dose(s) (in IU) and product batch numbers
- Details of BEs (if any) occurring under prophylactic treatment

Study drug consumption data (FVIII IU/kg per month, per year) per patient and in total (for patients on prophylactic treatment) will be evaluated.

Efficacy Assessment of Prophylactic Treatment

The efficacy of *Human-cl rhFVIII* in prophylactic treatment will be evaluated based on the frequency of spontaneous breakthrough bleeds per months under three times weekly or every other day prophylactic treatment and will be calculated and assessed as excellent, good, moderate or poor:

Excellent:	Less than 0.75 spontaneous BEs permonth
Good:	Between 0.75 and 1 spontaneous BEs per month
Moderate:	Between more than 1 and 1.5 spontaneous BEs per month
Poor:	More than 1.5 spontaneous BEs per month

The time period for prophylactic treatment will comprise the time periods between first prophylactic treatment with *Human-cl rhFVIII* until the administration of the last prophylactic treatment + 2 days or completion visit whatever comes first) minus time periods from start of a surgery until final assessment of the surgery, and minus time period of on demand treatment, if any.

The frequency of treatment will mainly depend on the patient's clinical situation and may vary from every other day to once weekly injections. In cases of inadequate response, *Human-cl rhFVIII* administration frequency or dose adjustments can be considered at Investigator's discretion.

The number of BEs counted for prophylactic treatment efficacy assessment will comprise all BEs starting during the time periods for prophylactic treatment defined above, i.e. BEs occurring between start of surgery until final assessment of the surgery will not be included in the prophylactic treatment assessment.

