- **Efficacy: Per Protocol (PP) analysis population**: All subjects in the ITT analysis population who completed the trial without significantly violating the inclusion/exclusion criteria or other aspects of the protocol considered to potentially affect the efficacy results.
Especially the following subjects will be excluded from this population:
 - Subjects who violate the following inclusion criteria:
 - severe haemophilia A (FVIII:C < 1%; historical value as documented in subject records),
 - no previous treatment with FVIII concentrate or other blood products containing FVIII
 - Subjects who fulfil at least one of the following exclusion criteria:
 - other coagulation disorder than haemophilia A
 - severe liver or kidney disease (ALT and AST levels >5 times of upper limit of normal, creatinine >120 $\mu\text{mol/L}$),
 - concomitant treatment with any systemic immunosuppressive drug,
 - Subjects who use concomitant medication that may confound study results, like e.g. alpha-interferon or prednisone
 - Subjects with significant non-compliances with the protocol like for example non-compliance to complete the diary in a proper manner or more than 30% of haemostatic efficacy assessments missing.

- Subjects with dosing or treatment errors like e.g. the use of other FVIII products (except for emergencies) or several *unexplained* and significant deviations from the recommended dose regimen.
- Subjects for whom less than a minimum of inhibitor tests is available*
- Patients with less than 95 days of exposure to *Human-cl rhFVIII*.

*Defined during Data Review Meeting for the interim analysis on April 7, 2016:

if less than 1 inhibitor test is available for any of the following periods:

- baseline, if first result of inhibitor screening after first exposure to the study drug is positive (it cannot be assured that the patient is a PUP),
- between ED2 and ED20,
- between ED21 and ED50.

- Population of subjects on prophylactic treatment schedule (PROPH): All subjects in the ITT population who have at least one prophylactic treatment. Only data under prophylaxis will be used for the analyses.
- Per-protocol population of subjects on prophylactic treatment schedules (PROPH-PP): All subjects in the PP population who have at least 95 EDs of treatment and who have no significant dosing or treatment errors, like e.g. unexplained interruptions of the prophylaxis with *Human-cl rhFVIII*.

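### The SAP rates prophylaxis on all dosing frequencies without saying so, while the protocol is inconsistent on whether the rating is confined to three-times-weekly or every-other-day dosing

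*SAP*

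**What the plan says.** **Protocol, restricted wording.** Section 7.2.2.1 introduces the excellent, good, moderate and poor categories as an assessment of the "frequency of spontaneous breakthrough bleeds per months under three times weekly or every other day prophylactic treatment". Section 3.3.3 (Target Parameters) carries the same condition: "Frequency of spontaneous breakthrough bleeds under three times weekly or every other day prophylactic treatment".

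**Protocol, unrestricted wording.** Directly under the scale, 7.2.2.1 sets the rated period. It runs from the first prophylactic dose "until the administration of the last prophylactic treatment + 2 days or completion visit", less surgery and on-demand time. The bleeds counted "comprise all BEs starting during the time periods for prophylactic treatment defined above". The same section allows the frequency to range from every other day down to once weekly. The secondary objective in 2.2 and the endpoint in 3.1.2.1 speak of prophylactic treatment with no frequency condition. Section 3.1.2.1 refers to 7.2.2.1 for detail.

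**Step-up.** Protocol 5.4 gives as examples starting with every-other-day injections "or with once weekly injections, followed by twice and three times weekly, and every other day treatment".

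**SAP.** Section 3.4.1 keeps the four categories and their cut-offs but states the endpoint as "Monthly rate of spontaneous break-through bleeds during time of prophylactic treatment assessed as excellent, good, moderate or poor by the following scale". All spontaneous bleeds in the prophylaxis period count. The PROPH set in SAP 5.1 is "All subjects in the ITT population who have at least one prophylactic treatment. Only data under prophylaxis will be used for the analyses". In the definition of on-demand periods, SAP 5.1 treats a patient as under prophylaxis for 14 days after each prophylactic dose, so once- and twice-weekly phases fall inside.

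**Breakdown.** Protocol 9.2.3, SAP 9.2 and SAP tables 14.2.19.1.2-6 add bleeding rates by intensity of prophylaxis.

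**The concern.** The cut-offs of 0.75, 1 and 1.5 spontaneous bleeds per month are the same in both documents, but the time they are applied to can be read in two ways. Under the restricted wording, the rating describes prophylaxis given three times weekly or every other day. Under the SAP, it describes whatever mix of frequencies each patient received. That mix depends on whether the patient was stepped up and how quickly, which 5.4 leaves to the clinical situation and the investigator. Two patients with the same bleed rate on the same regimen could then be rated differently because their step-up phases differed in length.

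A reader who takes the meaning of the rating from the wording of 3.3.3 or 7.2.2.1 would misread the reported result. The SAP marks other changes openly, for example the inhibitor-free analyses it labels as additions to its version 2.0. It says nothing about the missing frequency condition.

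**Working it through.** The documents give no step-up durations and no expected bleed rates, so there is no planned figure to reproduce. The check is a comparison of texts followed by an illustration on assumed inputs.

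**1. Comparison of texts**

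| Place | Frequency condition? |
|---|---|
| Protocol 2.2 and 3.1.2.1 (objective, endpoint) | No |
| Protocol 3.3.3 (target parameter) | Three times weekly or every other day |
| Protocol 7.2.2.1, sentence introducing the rating | Three times weekly or every other day |
| Protocol 7.2.2.1, period and bleeds counted | No |
| Protocol 9.2.1, PROPH and PROPH-PP | No |
| SAP 3.4.1, endpoint and period | No |
| SAP 5.1, PROPH, PROPH-PP and PROPHcont | No |

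The condition is stated twice in the protocol and contradicted within 7.2.2.1. The SAP follows the counting rule and leaves out the condition.

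**2. Does the intensity table recover the restricted rate?**
Only if one of its classes is exactly three-times-weekly or every-other-day time. Neither document defines the classes. The intensity that SAP 5.1 and 9.1 do define is intensity of treatment, through peak treatment moments, which is not dosing frequency. Protocol 9.2.1 lists classes of prophylactic treatment by amount and frequency, but for inhibitor incidence, and the SAP 5.1 list does not carry them over.

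**3. Share of time outside the named regimens (assumed)**
Assume 100 exposure days (EDs), all prophylactic, with *a* weeks once weekly, *a* weeks twice weekly and the rest three times weekly. Step-up uses *a* + 2*a* EDs. The share is *f* = 2*a* / [2*a* + (100 − 3*a*)/3].

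- 4+4 weeks: 12 EDs; 88/3 = 29.3 weeks; *f* = 8/37.3 = 21%
- 8+8 weeks: 24 EDs; 76/3 = 25.3 weeks; *f* = 16/41.3 = 39%
- 12+12 weeks: 36 EDs; 64/3 = 21.3 weeks; *f* = 24/45.3 = 53%

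With every-other-day dosing (3.5 per week) after step-up, the shares are 24%, 42% and 57%. A patient who starts on every-other-day dosing has *f* = 0.

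**4. Effect on the rating (assumed rates)**
All-time rate = *f* × step-up rate + (1 − *f*) × full-regimen rate.

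- Full regimen 0.6, step-up 1.2 per month: excellent becomes good at *f* = (0.75 − 0.6)/(1.2 − 0.6) = 25%. At *f* = 40% the rate is 0.48 + 0.36 = 0.84.
- Full regimen 0.3, step-up 1.2: the change comes at *f* = (0.75 − 0.3)/(1.2 − 0.3) = 50%.
- Full regimen 0.3, step-up 0.6: no change at any *f*, since the rate never exceeds 0.6.
- First pair reversed (full regimen 1.2, step-up 0.6): at *f* = 40% the rate is 0.24 + 0.72 = 0.96, so moderate becomes good.

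Pooling can therefore worsen the rating, improve it or leave it alone.

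**The case against.** The strongest reply is that the SAP implements the operative rule. The counting rule in 7.2.2.1 removes only surgery and on-demand time, and the endpoint in 3.1.2.1 has no frequency condition. A reader might infer from the rating sentence that the protocol rates prophylaxis only under the two named regimens, that its secondary endpoint is never computed, or that the SAP rates a different regimen. The documents do not support these readings. The endpoint is computed under one of the protocol's two definitions, and the pooled time includes the named regimens. Nor did the SAP strip a frequency condition from the analysis sets: the protocol's PROPH and PROPH-PP never had one, and PROPHcont is new in the SAP.

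A second reply is that a restricted rate has its own weakness. Protocol 5.4 and 7.2.2.1 allow frequency to be adjusted for inadequate response, so achieved frequency can depend on bleeding. A patient who stays on once- or twice-weekly dosing would have no restricted rating. This is a good argument against making the restricted rate the only headline.

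Third, the analysis is descriptive and the numerical examples rest on assumptions. That is true, and it limits the weight of the point.

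None of these replies removes the contradiction in the protocol, the SAP's silence about it, or the undefined intensity classes.

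**Conclusion.** The concern holds as an unreconciled definition. The protocol states the restricted bleed frequency twice and a contradictory counting rule once. The SAP takes the all-time reading without declaring it, and the planned intensity table does not guarantee that the restricted rate will be available.

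The size and direction of any effect cannot be determined from the documents. The range of 21% to 53% of prophylaxis time depends on assumed step-up lengths and on three-times-weekly dosing for the remaining exposure days. Whether a category changes depends on assumed bleed rates, and in one of the cases shown it never does. Low frequency may raise bleeding while very young age may lower it, so no direction should be presumed. For a descriptive secondary endpoint, this should be corrected, but it does not threaten the primary immunogenicity result.

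**What to change.** 1. Reconcile protocol 3.3.3 and 7.2.2.1 with SAP 3.4.1, and state which prophylaxis time the rating uses.
2. In SAP 3.4.1 and 9.2, report the monthly spontaneous-bleed rate and its rating twice: for all prophylaxis time, and for time on three-times-weekly or every-other-day dosing. Derive the frequency actually given from the recorded infusion dates, by a rule written into the SAP.
3. Define the intensity classes for tables 14.2.19.1.2-6 by dosing frequency: once weekly, twice weekly, and three times weekly or every other day.
4. If the all-time rate leads, declare the departure from the wording of 3.3.3 and 7.2.2.1.

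The cost is SAP wording and one derived variable, since infusion dates and times are already collected. The restricted rate will rest on less time and fewer patients. It should carry a note that dosing frequency can itself respond to bleeding. No change to any dosing rule is proposed.

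The same edit should settle a related mismatch: the rated period ends 2 days after the last prophylactic dose in protocol 7.2.2.1 but 14 days after it in SAP 3.4.1 (in both, the completion visit if earlier).
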